### 9.1.7 Independent Data Monitoring Committee

#### Part B Only

An independent data monitoring committee (IDMC) will be formed using the Cystic Fibrosis Foundation Data Safety Monitoring Board. The IDMC objectives and operational details will be defined in a separate document (IDMC Charter), which will be finalized before the first subject is screened. The IDMC will conduct regular planned reviews of study data as outlined in the IDMC Charter.

### 9.2 Method of Assigning Subjects to Treatment Groups

This is an open-label study. Randomization is not required because all subjects will be treated identically. An interactive web response system (IWRS) will be used to dispense dosage based on subject weight at Day 1.

### 9.3 Rationale for Study Elements

#### 9.3.1 Study Design

The subjects studied are from the population that is expected to benefit from treatment with VX-445/TEZ/IVA.

**Part A**

The open-label design is considered adequate to evaluate the PK and safety of VX-445/TEZ/IVA in this pediatric population. Evaluation of a single-dose level is sufficient for the assessment of VX-445/TEZ/IVA across subjects in different weight ranges to confirm the doses and appropriate weight cutoff for Part B.

**Part B**

Part B is designed to evaluate the long-term safety in the pediatric CF population. This design is in harmony with guidelines for the study of human subjects, especially children, and balances safety concerns with potential benefits for the individual.

**9.3.2 Study Population****Parts A and B**

Patients with an F/MF genotype (30% of all patients with CF) generally have severe disease and do not have approved CFTR modulator therapy available to them; clinical studies of LUM/IVA and TEZ/IVA did not show improvement in lung function in this patient population. Without an available CFTR modulator therapy, patients with F/MF genotypes must continue to rely on adjunctive treatments and symptomatic therapies to manage their severe CF disease. Patients with an F/F genotype also have continuing unmet need despite the availability of CFTR modulators for this population. Based on in vitro data and preliminary clinical data, VX-445/TEZ/IVA is expected to provide a clinically relevant advantage over currently available treatments for F/MF and F/F patients.

Given the progressive nature of CF, there is a strong rationale for treating patients earlier in life. Experience with CFTR modulators in pediatric subjects  $\geq 6$  to  $\leq 11$  years of age, including with TEZ/IVA, suggests that the safety profile of VX-445/TEZ/IVA will be similar in children and adults, which supports evaluation of VX-445/TEZ/IVA in pediatric subjects in the present study.

**9.3.3 Study Drug Dose and Duration****Parts A and B****VX-445 Dosage**

A VX-445 dose of 200 mg qd was evaluated in Phase 3 studies of adult and adolescent ( $\geq 12$  years of age) CF subjects with F/MF and F/F genotypes. The 200-mg dose was selected based on an assessment of the benefit-risk profile from Phase 2 Study VX16-445-001 (Study 445-001) which evaluated a range of VX-445 doses (50 mg qd, 100 mg qd, and 200 mg qd) in TC with TEZ/IVA in CF subjects with F/MF and F/F genotypes. In Study 445-001, the TC was generally safe and well tolerated in all VX-445 dose groups. Subjects with F/MF genotypes who received the VX-445 200 mg qd TC demonstrated a clinically meaningful improvement in ppFEV1 (within-group mean [SE] absolute change of 13.8 [1.4] percentage points from baseline [ $P < 0.0001$ ], compared with a mean absolute change of 0.0 [2.0] percentage points in subjects who received placebo [ $P = 0.9943$ ]). A similar magnitude of change was observed in subjects with F/F genotypes compared with subjects who received the active comparator of TEZ/IVA.

**Part A**

The VX-445 dose of 100 mg qd selected for evaluation in Part A was determined based on population-PK modeling utilizing data from adults and simulating exposures over a range of

body weights typical for a population of 6- to <12-year-olds, ranging from 15 to 50 kg. The simulations indicate that a VX-445 dose of 100 mg qd is predicted to provide exposures that would not exceed the exposures observed in adults dosed with 200 mg qd. Hence, the VX-445 100-mg qd dose was predicted to be safe and was selected to be evaluated in Part A for all subject weight groups.

## **Part B**

For Part B, subjects in the higher weight range will be administered VX-445 200 mg qd. The appropriate weight cutoff for the switch from 100 mg qd to 200 mg qd was determined based on population-PK modeling which was updated with preliminary PK data from Part A and data from studies conducted in adult and adolescent CF subjects. For Part B, a VX-445 dose of 100 mg qd will be evaluated in subjects weighing <30 kg. In subjects weighing  $\geq 30$  kg, a VX-445 dose of 200 mg qd will be evaluated. These doses are predicted to be safe based on PK data from Part A, data obtained from adults in the Phase 2 Study 445-001, and preliminary data obtained from adults and adolescents (12- to <18-year-olds) in Phase 3 Studies 445-102 and 445-103.

## **TEZ and IVA Dosages**

TEZ will be administered as 50 mg qd and IVA will be administered as 75 mg every 12 hours (q12h) in all subjects in Part A and in subjects weighing <30 kg in Part B. In Part B, doses of TEZ 100 mg qd and IVA 150 mg q12h will be administered in subjects weighing  $\geq 30$  kg. The dosages and weight cutoff in Part B were selected based on an evaluation of PK and safety of TEZ/IVA in CF subjects 6 to 11 years of age in Part A of Study VX15-661-113 (Study 661-113). Part B of Study 661-113 assessed the safety and efficacy of TEZ/IVA at these doses in CF subjects 6 to 11 years of age.

## **Part A**

### Duration of Dosing

The 15-day duration of dosing was chosen to provide an adequate assessment PK, safety, and tolerability of VX-445/TEZ/IVA before exposing subjects to a longer duration of treatment in Part B.

## **Part B**

### Duration of Dosing

The 24-week duration of dosing was chosen to provide an adequate assessment of long-term safety.

## **9.3.4 Rationale for Study Assessments**

### **Parts A and B**

The PK, safety, efficacy, and PD assessments are standard parameters for clinical studies in drug development and are generally recognized as reliable, accurate, and relevant to the study of subjects with CF. Baseline and follow-up ophthalmologic examinations are recommended for monitoring of pediatric patients treated with IVA-containing drug regimens, and have been added to the standard safety assessments.

LCI (Part B only) is a measure of ventilation inhomogeneity assessed by multiple-breath washout (MBW) that is based on tidal breathing techniques that have been evaluated in patients as young as infants. Studies have shown that LCI correlates with forced expiratory volume in 1 second (FEV1) in its ability to measure airway disease and can detect lung disease at an earlier stage than spirometry. Furthermore, data from Study VX10-770-106 in CF patients with an FEV1>90% showed LCI to be a more sensitive outcome measure than FEV1.

The Modified Facial Hedonic Scale questionnaire (Part B only) will evaluate the subject’s acceptance of the administered study drug dose. The convenience, ease of administration, and perception of the child’s acceptance of the study drug by the parent/caregiver will also be evaluated. All subjects will be observed for their facial expressions and the reaction will be scored using a visual analog scale; any spontaneous comments in regards to likes or dislikes will also be noted. Interviews will be conducted on a one-on-one basis in the clinic setting.

**9.4 Study Restrictions**

**9.4.1 Prohibited Medications**

**Parts A and B**

Table 9-2 lists prohibited medications. A non-exhaustive list of study prohibitions and cautions for medication will be provided in the Study Reference Manual.

**Table 9-2 Prohibited Medications**

Medication	Timing of Restriction		Rationale
	Start of Restriction	End of Restriction	
Moderate and strong CYP3A inducers	None allowed within 14 days before the first dose of the study drug on Day 1	None allowed through completion of study participation	VX-445, TEZ, and IVA are metabolized extensively via CYP3A4. Therefore, use of moderate and strong inducers and inhibitors of CYP3A, which have the potential to alter the exposure of VX-445, TEZ, or IVA, will be prohibited.
Moderate and strong CYP3A inhibitors (except ciprofloxacin) a	None allowed within 14 days before the first dose of the study drug on Day 1	None allowed through completion of study participation	
CFTR modulators	None allowed	None allowed	These agents may confound the results of this

**Table 9-2 Prohibited Medications**

Medication	Timing of Restriction		Rationale
	Start of Restriction	End of Restriction	
(investigational or approved), except for study drugs	within 28 days before the first dose of the study drug on Day 1	until after the last dose of study drug	study.

CYP: cytochrome P450; IVA: ivacaftor; TEZ: tezacaftor

a Ciprofloxacin is not a moderate CYP3A inhibitor on the basis of results of a drug-drug interaction study conducted with IVA, a sensitive CYP3A substrate (Kalydeco [ivacaftor] US Package Insert).

## 9.5 Prior and Concomitant Medications

### Parts A and B

Information regarding prior and concomitant medications, including CF medications, other medications, and herbal and naturopathic remedies, will be collected from each subject's source documentation for medications taken within 56 days before the Screening Visit through completion of study participation, as defined in Section 9.1.6.

For subjects who are screened but are not subsequently enrolled, details of prior medication will be documented only in the subjects' source documents.

- Subjects should remain on a stable treatment regimen for their CF from 28 days before the Day 1 Visit through completion of study participation. Stable treatment regimen is defined as the current treatment regimen for CF that subjects have been following for at least 28 days before the Day 1 Visit. Subjects should not initiate long-term treatment with new medication from 28 days before the Day 1 Visit through completion of study participation. Guidelines for stable treatment regimens for CF are as follows:
  - o Subjects who are taking inhaled tobramycin or other chronically inhaled antibiotics should remain on that regimen throughout the study.
  - o Subjects who cycle onto and off of an inhaled antibiotic should continue on their prior schedule. The timing of the first dose of study drug on the Day 1 Visit should be synchronized as closely as possible (e.g., not more than  $\pm 3$  days) to the first day in the cycle onto the inhaled antibiotic.
  - o Subjects who alternate between 2 different inhaled antibiotics should remain on the same cycling schedule during the study. The timing of the first dose of study drug on the Day 1 Visit should be synchronized as closely as possible (e.g., not more than  $\pm 3$  days) to the first day in the cycle onto 1 of the inhaled antibiotics.
- Subjects may receive doses of prednisone or prednisolone of up to 10 mg/day chronically, or up to 60 mg daily for up to 5 days.
- VX-445 may inhibit OATP1B1 and OATP1B3, which may increase the exposure of medicinal products that are substrates for these transporters. Substrates such as statins, glyburide, nateglinide, and repaglinide should be used with caution.

- IVA is a weak inhibitor of P-glycoprotein (P-gp). Administration of IVA may increase systemic exposure of medicinal products that are sensitive substrates of P-gp, which may increase or prolong their therapeutic effect and adverse reactions. Digoxin or other substrates of P-gp with a narrow therapeutic index, such as cyclosporine, everolimus, sirolimus, and tacrolimus, should be used with caution and appropriate monitoring.
- IVA may inhibit CYP2C9; therefore, during coadministration with warfarin, additional monitoring of the international normalized ratio is recommended. Other medicinal products that are CYP2C9 substrates for which exposure may be increased include glimepiride and glipizide; these should be used with caution.
- Information about bronchodilator use during the study will be collected and documented. Subjects who are using a bronchodilator should have their spirometry assessments performed according to the guidelines provided in Section 11.4.1.

## 9.6 Administration

### 9.6.1 Dosing

#### Part A

On Day 1 through Day 15, VX-445/TEZ/IVA will be orally administered with water. On Day 15, only the morning dose of VX-445/TEZ/IVA will be administered.

Study drug should be administered within approximately 30 minutes of the start of a fat-containing snack or meal, such as a standard “CF” meal or snack according to the following guidelines:

1. Morning dose of study drug will be administered at the site on Days 1, 2, 8, and 15.
2. Study drug will be administered after all predose assessments have been performed.
3. All doses of study drug (morning and evening, as applicable) should be administered at approximately every 12 hours ( $\pm$  1 hour) on each dosing occasion (e.g., if the morning doses of study drug are administered at 08:00 hour on Day 1, all subsequent morning doses should be administered between 07:00 hour and 09:00 hour).
4. Study drug tablets will be administered within 5 minutes of each other.
5. Study drug will be administered with approximately 240 mL (approximately 1 cup, 8 ounces, or half a pint) of water.
6. At the Day 1 Visit, all subjects will be observed for 4 hours after the morning dose of the study drug.
7. The date, amount taken, and time of study drug administration including whether food was taken with each dose, will be recorded for 2 days before PK sample collection and on the days of PK sample collection.

#### Part B

Study drug tablets will be administered orally as shown in [Table 9-3](#). A review of safety, tolerability, and available PK data will be completed by an internal Vertex team after Part A and the dose chosen for Part B will be confirmed by this review.

**Table 9-3 Study Drug Administration, Part B**

Subject Weight at Day 1	Tablet Strength	Time	Number of Tablets Taken
<30 kg	50-mg VX-445/25-mg TEZ/37.5-mg IVA	AM	2 tablets
	75-mg IVA	PM	1 tablet
≥30 kg	100-mg VX-445/50-mg TEZ/75-mg IVA	AM	2 tablets
	150-mg IVA	PM	1 tablet

IVA: ivacaftor; TEZ: tezacaftor

Study drug should be administered with a fat-containing meal or snack, such as a standard “CF” meal or snack or a standard meal according to the following guidelines:

1. It is recommended that the dose be taken within 30 minutes of the start of the meal or snack.
2. All doses of study drug (morning and evening, as applicable) should be administered at approximately every 12 hours ( $\pm$  2 hours) on each dosing occasion (e.g., if the morning doses of study drug are administered at 08:00 hour on Day 1, all subsequent morning doses should be administered between 06:00 hour and 10:00 hour).
3. At the Day 1 Visit, all subjects will be observed for 4 hours after the morning dose of the study drug.
4. The date, amount taken, and time of study drug administration including whether food was taken with each dose, will be recorded for 2 days before PK sample collection and on the days of PK sample collection.
5. On days of scheduled visits (Day 1, Day 15, Weeks 4, 8, 12, and 16), the morning dose of study drug will be administered at the site after predose assessments have been completed. The meal or snack will be provided by the site for the morning dose of study drug.
6. For visits after the Day 1 Visit, subjects will be instructed to bring all used and unused study drug to the site; study drug will be dispensed at each visit, as appropriate.
7. At the Week 24 Visit, the morning dose of study drug will NOT be administered. The last dose of study drug will be the evening dose administered the day before the Week 24 Visit.

### 9.6.2 Missed Doses

#### Parts A and B

If 6 hours or less have passed since the missed morning or evening dose, the patient should take the missed dose as soon as possible and continue on the original schedule.

**Morning dose:** If more than 6 hours have passed since the missed **morning** dose, the patient should take the missed dose as soon as possible and should not take the evening dose.

**Evening dose:** If more than 6 hours have passed since the missed **evening** dose, the patient should not take the missed dose. The next scheduled morning dose should be taken at the usual time.

Morning and evening doses should not be taken at the same time.

## 9.7 Dose Modification for Toxicity

### Parts A and B

Modifications of the study drug dose are prohibited. Should any unacceptable toxicity arise, individual subjects will be withdrawn from the study and dosing will cease.

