## **9.1.2 Treatment Period**

### **Parts A and B**

The Treatment Period will last approximately 15 days in Part A and 24 weeks in Part B. Study drug administration details are provided in Section 9.6.

Subjects who prematurely discontinue study drug treatment will remain in the study from the time of discontinuation of study drug treatment through the last scheduled study visit and complete the assessments for all study visits, as described in Section 9.1.4.

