### 9.1.4 Early Termination of Treatment

#### Parts A and B

If a subject prematurely discontinues study drug treatment, an Early Termination of Treatment (ETT) Visit should be scheduled as soon as possible after the decision to discontinue treatment. Subjects who prematurely discontinue treatment will also be required to complete the Safety Follow-up Visit ([Table 3-2](#) for Part A and [Table 3-4](#) for Part B), if applicable (Section 9.1.3).

If a subject withdraws from the study and also withdraws consent or assent, no further assessments will be performed. Vertex may retain and continue to use any data and samples collected before such withdrawal of consent or assent.

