#### Part B

If the ETT Visit occurs 3 weeks or later following the last dose of study drug, then the ETT Visit will replace the Safety Follow-up Visit, and a separate Safety Follow-up Visit will not be required.

Subjects who prematurely discontinue study drug treatment will continue to complete all scheduled study visits for assessments following completion of the ETT Visit, as detailed in [Table 3-4](#).

Subjects who prematurely discontinue treatment in Part B are not eligible to enroll in the optional open-label extension safety study.

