#### Part A

- For subjects who complete the Treatment Period: the Safety Follow-up Visit
- For subjects who prematurely discontinue study drug treatment but do not withdraw consent (and assent, as applicable): the latest of the Day 15 Visit, ETT Visit, or Safety Follow-up Visit
- For subjects who withdraw consent or assent: date of withdrawal of consent or assent, whichever is earlier (Section 9.9)

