#### Part B

- For subjects who complete the Treatment Period and enter an open-label extension safety study within 28 days of the Week 24 Visit: the Week 24 Visit
- For subjects who complete the Treatment Period and do not enter an open-label extension safety study within 28 days of the Week 24 Visit: the Safety Follow-up Visit
- For subjects who prematurely discontinue study drug treatment but do not withdraw consent (and assent, as applicable): the latest of the Week 24 Visit, ETT Visit, or Safety Follow-up Visit (if required)
- For subjects who withdraw consent or assent: date of withdrawal of consent or assent, whichever is earlier (Section 9.9)

If subjects are lost to follow-up (Section 9.1.5), the date of completion of study participation will be defined as the date of the last contact.

The end of study is defined in Section 13.2.8.

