### **9.9 Removal of Subjects**

#### **Parts A and B**

Subjects may withdraw from the study at any time at their own request. Subjects may be withdrawn from study drug treatment at any time at the discretion of the investigator or Vertex for safety, behavior, noncompliance with study procedures, or administrative reasons. If a subject has been withdrawn from study drug treatment, the subject will continue to be followed, provided that the subject has not withdrawn consent (and assent, as applicable).

In addition, a subject must be discontinued from study drug treatment if the subject meets any of the following criteria:

- Has a screening *CFTR* genotype that does not confirm study eligibility if a previous *CFTR* genotype laboratory report was used to establish eligibility. These subjects must be discontinued from the study (Section 8.1)
- Meets any of the stopping (discontinuation) criteria (Section 9.8)
- Becomes pregnant (Section 11.5.6.2)

Subjects who discontinue study drug treatment should return for study assessments, as noted in Section 9.1.4.

If a subject does not return for a scheduled visit, reasonable effort will be made to contact the subject. In any circumstance, reasonable effort will be made to document subject outcome. The investigator will inquire about the reason for withdrawal, request that the subject return all unused investigational product(s), request that the subject return for an ETT Visit and Safety Follow-up Visit, if applicable (see Section 9.1.4), and follow up with the subject regarding any unresolved AEs.

If the subject withdraws consent or assent for the study, no further assessments will be performed. Vertex may retain and continue using the study data and samples after the study is over, and may use the samples and information in the development of the study compound, and for other drugs and diagnostics, in publications and presentations, and for education purposes. If the subject withdraws from the study, the study data and samples collected will remain part of the study. A subject will not be able to request the withdrawal of his/her information from the study data. A subject may request destruction of the samples collected from him/her during the study as long as those samples can be identified as his/her samples.

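### Protocol 9.7 withdraws subjects with unacceptable toxicity from the study, while 9.1.2, 9.1.4, 9.1.6 and 9.9 take them off study drug only and keep following them

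*Protocol*

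**What the plan says.** Protocol 9.7 (Dose Modification for Toxicity, Parts A and B) prohibits dose changes and then states: "Should any unacceptable toxicity arise, individual subjects will be withdrawn from the study and dosing will cease". The sentence is mandatory and names two separate actions, leaving the study and stopping drug.

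Other sections of the same protocol treat a safety stop differently:

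- 9.1.2 (both Parts): "Subjects who prematurely discontinue study drug treatment will remain in the study", through the last scheduled visit.
- 9.1.4 (both Parts): an Early Termination of Treatment (ETT) Visit, and then "Subjects who prematurely discontinue treatment will also be required to complete the Safety Follow-up Visit", where applicable. For Part B it adds: "Subjects who prematurely discontinue study drug treatment will continue to complete all scheduled study visits for assessments following completion of the ETT Visit".
- 9.1.4 on when assessments end: "If a subject withdraws from the study and also withdraws consent or assent, no further assessments will be performed".
- 9.1.6: for subjects who stop drug without withdrawing consent, participation in Part A is complete at "the latest of the Day 15 Visit, ETT Visit, or Safety Follow-up Visit". Part B has the same rule with Week 24 in place of Day 15.
- 9.9 (Removal of Subjects): "Subjects may be withdrawn from study drug treatment at any time at the discretion of the investigator or Vertex for safety", among other reasons. Such subjects continue to be followed unless consent or assent is withdrawn.

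SAP 9.3.2 and 9.3.2.2.2 state that the Part B efficacy analyses, including the ppFEV1 mixed model, use measurements taken after treatment discontinuation. SAP 9.4 bases all safety analyses on the treatment-emergent (TE) Period. SAP 9.1 ends that period at 28 days after the last dose or at completion of participation, whichever comes first.

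**The concern.** A site that meets unacceptable toxicity has two instructions that cannot both be followed. Under 9.7 the child leaves the study. Under 9.9, with 9.1.2 and 9.1.4, the child leaves study drug and keeps attending visits. 9.1.6 has no completion category for a child removed for toxicity whose family has not withdrawn consent, so a literal 9.7 withdrawal has no defined end-of-participation date.

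The data at stake are the off-drug visits up to Week 24, and they would be lost selectively in children with toxicity. The SAP's mixed model is specified to use those values and otherwise assumes data are missing at random. Adverse events after the TE Period, which SAP 9.4.1 puts in the listings, would also go uncollected. These children cannot enter the open-label extension (9.1.4, Part B), so that route to later observation is closed. SAP 9.2.1 counts treatment discontinuation and study discontinuation separately. Two sites could therefore code the same event differently, each following the protocol.

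**Working it through.** No figure in the plan depends on this wording. The Part B detection probabilities (Protocol Table 12-1) reproduce, for example 1 − 0.95^45 = 0.9006 against the stated 90.0%, and they do not change.

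**Is there a conflict?** 9.7 names toxicity and removes the subject from the study. 9.9 names safety and removes the subject from study drug treatment, with follow-up continuing. 9.1.2 keeps any subject who stops drug in the study and makes no exception for toxicity. The only case in which 9.9 requires discontinuation from the study itself is an ineligible genotype, which is not a toxicity reason. No sentence limits 9.7 to study drug.

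**What would literal use of 9.7 cost a Part B child?**

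Inputs from SAP Table 12-2:
- Target days: Week 4 = 29, Week 8 = 57, Week 12 = 85, Week 16 = 113, Week 20 = 141, Week 24 = 169.
- Spirometry windows: Week 4 (22,43], Week 8 (43,71], Week 12 (71,99], Week 16 (99,141], Week 24 (141,183]. Weight, height and BMI use the same windows.
- Sweat chloride and LCI windows: Week 4 (22,57], Week 12 (57,127], Week 24 (127,183].

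Inputs from Protocol Table 3-4: spirometry, weight, height and BMI are done at both ETT and Safety Follow-up. Sweat chloride and multiple-breath washout are done at ETT but not at Safety Follow-up.

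Assumptions: all visits are attended through the last dose; ETT is on the last-dose day or one day later; Safety Follow-up is at last dose + 28 ± 7 days; nothing is collected after that. Day 15 is left out because it does not enter the average.

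| Last dose | ETT day | Safety Follow-up day | Spirometry window it falls in | ppFEV1 visits lost (of 5) | Sweat chloride / LCI visits lost (of 3) |
|---|---|---|---|---|---|
| Week 4, D29 | 29–30 | 50–64 | Week 8 | Weeks 12, 16, 24: 3 | Weeks 12, 24: 2 |
| Week 8, D57 | 57–58 | 78–92 | Week 12 | Weeks 16, 24: 2 | ETT D57 counts as Week 4: 2; D58 counts as Week 12: 1 |
| Week 12, D85 | 85–86 | 106–120 | Week 16 | Week 24: 1 | Week 24: 1 |
| Week 16, D113 | 113–114 | 134–148 | Week 16 to D141, Week 24 from D142 | 1 or 0 | Week 24: 1 |
| Week 20, D141 | 141–142 | 162–176 | Week 24 | 0 | ETT falls in Week 24: 0 |

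The Week 24 weight, height and BMI values are lost in the first three rows, lost or kept in the fourth, and kept in the fifth.

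If Safety Follow-up were skipped too, only ETT would remain after the last dose. The ppFEV1 losses would then be:
- D29: Weeks 8, 12, 16, 24 = 4
- D57: Weeks 12, 16, 24 = 3
- D85: Weeks 16, 24 = 2
- D113: Week 24 = 1
- D141: 1 if ETT is on D141 (Week 16 window), 0 if on D142 (Week 24 window)

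**Primary safety summaries.** TE Period end = min(last dose + 28, completion). Under 9.1.6 completion is no earlier than D169, and the latest case gives 141 + 28 = 169, so all 28 off-drug days count in every row. Under literal 9.7 with Safety Follow-up held s days after last dose and taken as completion, the loss is 28 − min(28, s). That is 0 for s ≥ 28 and at most 7 at s = 21. It reaches as much as 28 only if Safety Follow-up is skipped as well.

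**Gap after the TE Period.** 169 − (last dose + 28) = 112, 84, 56, 28 and 0 days for the five rows. This gap affects the adverse event listings and efficacy, not the TEAE tables.

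**The case against.** The other side is strong on intent. 9.7 is a two-sentence section about not changing the dose. The operative toxicity rules are in 9.8, where study drug is interrupted or discontinued, and 9.8.1 requires continued liver monitoring. 9.9 puts anyone meeting a 9.8 stopping criterion under discontinuation of study drug treatment, with return visits per 9.1.4. Under 9.1.4, leaving the study ends assessments only when consent or assent is also withdrawn. Section 13.1.1.2 also uses discontinuation from the study loosely, as one response to an abnormal result. A careful site would probably read 9.7 as stopping drug. That limits how often harm would follow, but it does not remove a mandatory sentence that says something else.

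The loss counts depend on a mixed reading, in which 9.7 is literal for scheduled visits while ETT and Safety Follow-up are honoured. Two cells turn on a single day (D57 against D58, and D141 against D142), so they are given as ranges.

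Three stronger readings are tempting but not supported:

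- *That 10.6 contradicts 9.9 in the same way.* 10.6 only asks the investigator to consider discontinuing from the study a subject who keeps missing doses. 9.9 permits withdrawal from treatment for noncompliance with study procedures. Two discretionary provisions with different triggers are loose wording, not a contradiction.
- *That the primary safety analysis is compromised.* The TE Period and the required Safety Follow-up Visit largely protect it. Follow-up of the triggering event is also required separately (9.8.1 for transaminases, 9.9, 13.1.1.7).
- *That the trial loses a definable amount of data.* No toxicity discontinuation rate is given.

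**Conclusion.** The inconsistency is real and is in current text: 9.7 conflicts with 9.1.2, 9.1.4, 9.1.6 and 9.9. The follow-up design in those four sections is sound; 9.7 is the outlier.

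The consequence is modest and conditional on a site following 9.7 to the letter. For last dose at Week 4 / 8 / 12 / 16 / 20 with Safety Follow-up held, an affected Part B child loses 3 / 2 / 1 / 0–1 / 0 of five ppFEV1 visits and 2 / 1–2 / 1 / 1 / 0 of three sweat chloride and LCI2.5 visits. The Week 20 ppFEV1 entry becomes 0–1 if Safety Follow-up is also missed. These endpoints are secondary and their P-values nominal (SAP 9.3.2). The loss is sized per child and for Part B only, with no claim about the study as a whole. It still merits correction, because the missing values would come from the children whose course after stopping drug is of most interest.

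**What to change.** In 9.7, replace the part of the second sentence that removes subjects from the study and stops dosing, so that it reads: individual subjects will be *withdrawn from study drug treatment and followed per Sections 9.1.2, 9.1.4 and 9.9*.

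Optional tidying: in 10.6, refer to discontinuing study drug treatment, so that the protocol uses one term throughout.

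The cost is a few words at the next protocol amendment. The follow-up visits are already in Table 3-4. Stopping criteria, sample size, visit schedule and SAP stay as they are.
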